APPENDIX A
Performance Status Criteria

ECOG Performance Status Scale		Karnofsky Performance Scale	
Grade	Descriptions	Percent	Description
0	Normal activity. Fully active, able to carry on all pre-disease performance without restriction.	100	Normal, no complaints, no evidence of disease.
		90	Able to carry on normal activity; minor signs or symptoms of disease.
1	Symptoms, but ambulatory. Restricted in physically strenuous activity, but ambulatory and able to carry out work of a light or sedentary nature (e.g., light housework, office work).	80	Normal activity with effort; some signs or symptoms of disease.
		70	Cares for self, unable to carry on normal activity or to do active work.
2	In bed <50% of the time. Ambulatory and capable of all self-care, but unable to carry out any work activities. Up and about more than 50% of waking hours.	60	Requires occasional assistance, but is able to care for most of his/her needs.
		50	Requires considerable assistance and frequent medical care.
3	In bed >50% of the time. Capable of only limited self-care, confined to bed or chair more than 50% of waking hours.	40	Disabled, requires special care and assistance.
		30	Severely disabled, hospitalization indicated. Death not imminent.
4	100% bedridden. Completely disabled. Cannot carry on any self-care. Totally confined to bed or chair.	20	Very sick, hospitalization indicated. Death not imminent.
		10	Moribund, fatal processes progressing rapidly.
5	Dead.	0	Dead.

APPENDIX B
Subject's Study Drug Diary

CTEP-assigned Protocol # _____
Local Protocol # _____

SUBJECT'S STUDY DRUG DIARY – CEDIRANIB

Today's date _____ **Subject Name** _____ *(initials acceptable)* **Subject Study ID** _____

INSTRUCTIONS TO THE SUBJECT:

- Complete one form for each 4 week-period while you take **cediranib**.
- You will take your dose of **cediranib** each day in the morning. You will take ____ 15 mg tablets, and ____ 20 mg tablets every morning. You can take cediranib at least 1 hour before you eat or 2 hours after you eat. If a dose of **cediranib** is missed, it should be taken as soon as possible on the same day. If it is missed for the entire day, it should not be made up.
- Record the date, the number of tablets of each size you took, and when you took them.
- If you have any comments or notice any side effects, please record them in the Comments column.
- Please return this form to your physician when you go for your next appointment.

Day	Date	Time of daily dose	# of tablets taken		Comments
			15 mg	20 mg	
1					
2					
3					
4					
5					
6					
7					
8					
9					
10					
11					
12					
13					
14					
15					
16					
17					
18					
19					
20					
21					
22					
23					
24					
25					
26					
27					
28					

Physician's Office will complete this section:

- Date subject started protocol _____
- Date subject was removed from study _____
- Subject planned total daily dose _____
- Total number of capsules taken this month (each size) _____
- Physician/Nurse/Data Manager's Signature _____

Subject's signature _____

SUBJECT'S STUDY DRUG DIARY – LENALIDOMIDE

Today's date _____

Subject's Name _____

Subject's Study ID _____

INSTRUCTIONS TO THE SUBJECT:

1. Complete one form for each 4 week-period while you take **lenalidomide**. Only one cycle of study drug may be dispensed each month.
2. You will take your dose of **lenalidomide** each day in the morning. You will take ____ 5 mg capsules. You may take the capsules with or without food as you wish.
3. **Lenalidomide** capsules should be swallowed whole, and should not be broken, chewed or opened. If a dose of **lenalidomide** is missed, it should be taken as soon as possible on the same day. If it is missed for the entire day, it should not be made up. If you cannot swallow lenalidomide, you may be able to take it via gastrostomy tube. Your doctor will explain the procedure.
4. If you take more than the prescribed dose of **lenalidomide**, you should seek emergency medical care if needed and contact study staff immediately.
5. Record the date, the number of capsules you took, and when you took them.
6. If you have any comments or notice any side effects, please record them in the Comments column.
7. Please return this form to your physician when you go for your next appointment.

Day	Date	Time of daily dose	# of capsules taken	Comments
			5 mg	
1				
2				
3				
4				
5				
6				
7				
8				
9				
10				
11				
12				
13				
14				
15				
16				
17				
18				
19				
20				
21				

Physician's Office will complete this section:

1. Date subject started protocol _____
2. Date subject was removed from study _____
3. Subject's planned total daily dose _____
4. Total number of capsules taken this month (each size) _____
5. Physician/Nurse/Data Manager's Signature _____

Subject's signature _____

APPENDIX C

Hypertension Monitoring and Management*

Grade (CTCAEv5.0)	Antihypertensive Therapy	Blood Pressure Monitoring	Cediranib Dose Modification
Grade 1 120-139 mmHg Systolic 80-89 mmHg Diastolic	None Baseline	Standard monitoring Consider diuretics	No Change
Grade 2- Mild 140-159 mmHg Systolic 90-99 mmHg Diastolic	Initiate BB or Initiate DHP CCB &/or Increase doses of existing medications until BP controlled or at maximum dose	Increased frequency of monitoring until stabilized	No Change
Persistent Moderate Hypertension 140-159 mmHg Systolic 90-99 mmHg Diastolic	Initiate BB or Initiate DHP CCB or ACEI or Vasodilator &/or Increase doses or number of medications until BP controlled or at maximum dose	Increased frequency of monitoring until stabilized (e.g., every 48 hours) Supervised by healthcare professional	If partial or no control and BP still in a moderate range for 24-48 hours, hold cediranib and add additional drugs, increasing to a maximum dose until hypertension controlled; monitor for hypotension. Decrease cediranib by 1 dose level
Grade 3- Severe ≥ 160 mmHg Systolic ≥ 100 mmHg Diastolic	Start immediate therapy with 2 drug combination including at least a DHP CCB Escalate doses to achieve optimal control of BP, up to the maximum dose If partial or no BP control, add additional drugs up to 4; increase to optimal or maximum doses of all drugs	Increased frequency of monitoring until stabilized (e.g., every 48 hours) Supervised by healthcare professional	Hold cediranib ; if control of BP in the Mild range, restart cediranib at the next lower dose level If partial or no control, decrease cediranib by another dose level or discontinue therapy per investigator Stop cediranib if hypertension is symptomatic, and hospitalize patient for management of BP
Grade 4 Hypertensive Crisis	Optimal management with intensive IV support in ICU	Hospitalize patient for management	Off protocol therapy, discontinue cediranib , and monitor closely for hypotension

Abbreviations: Dihydropyridine calcium-channel blockers (DHP-CCB), selective beta blockers (BB), Angiotensin Converting Enzyme Inhibitors (ACEI), Angiotensin II Receptor Blockers (ARB)
 
*See table below for suggested antihypertensive medications by class If patients require a delay of >2 weeks for management of hypertension, discontinue protocol therapy If patients require >2 dose reductions, discontinue protocol therapy Patients may have up to 2 drugs for management of hypertension prior to any dose reduction in cediranib 24-48 hours should elapse between modifications of antihypertensive therapy Hypertension should be graded using the NCI CTCAEv5.0
			

Oral Antihypertensive Medications: *Agents in bold characters are suggested as optimal choices to avoid or minimize potential drug-interactions with cediranib through CYP450.

Agent class	Agent	Initial dose	Intermediate dose	Maximum dose	Hepatic metabolism
Dihydro-pyridine Calcium-Channel Blockers (DHP CCB)	nifedipine XL	30 mg daily	60 mg daily	90 mg daily	CYP 3A4 substrate
	amlodipine	2.5 mg daily	5 mg daily	10 mg daily	CYP 3A4 substrate
	felodipine	2.5 mg daily	5 mg daily	10 mg daily	CYP 3A4 substrate and inhibitor
Selective β Blockers (BB)	metoprolol	25 mg twice daily	50 mg twice daily	100 mg twice daily	CYP 2D6 substrate
	atenolol	25 mg daily	50 mg daily	100 mg daily	No
	acebutolol	100 mg twice daily	200-300 mg twice daily	400 mg twice daily	Yes (CYP450 unknown)
	bisoprolol	2.5 mg daily	5-10 mg daily	20 mg daily	Yes (CYP450 unknown)
Angiotensin Converting Enzyme Inhibitors (ACEIs)	captopril	12.5 mg 3x daily	25 mg 3x daily	50 mg 3x daily	CYP 2D6 substrate
	enalapril	5 mg daily	10-20 mg daily	40 mg daily	CYP 3A4 substrate
	ramipril	2.5 mg daily	5 mg daily	10 mg daily	Yes (CYP450 unknown)
	lisinopril	5 mg daily	10-20 mg daily	40 mg daily	No
	fosinopril	10 mg daily	20 mg daily	40 mg daily	Yes (CYP450 unknown)
	Rarely used: perindopril	4 mg daily	none	8 mg daily	Yes, but not CYP450
	Rarely used: quinapril	10 mg daily	20 mg daily	40 mg daily	No
Angiotensin II Receptor Blockers (ARBs)	losartan	25 mg daily	50 mg daily	100 mg daily	CYP 3A4 substrate
	candesartan	4 mg daily	8-16 mg daily	32 mg daily	CYP 2C9 substrate
	irbesartan	75 mg daily	150 mg daily	300 mg daily	CYP 2C9 substrate
	telmisartan	40 mg daily	none	80 mg daily	Yes, but not CYP450
	valsartan	80 mg daily	none	160 mg daily	Yes, but not CYP450
α and β Blocker	labetolol	100 mg twice daily	200 mg twice daily	400 mg twice daily	CYP 2D6 substrate and inhibitor

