6.1.1 Management of Hypertension

Adverse event	NCI CTCAE v.5 grade	Management	Cediranib administration
Hypertension	Grade 1 Systolic 120-139 mmHg or diastolic 80-89 mmHg	Consider increased BP monitoring	No change
	Grade 2-Mild Stage 1 hypertension: (140-159 mmHg Systolic or 90-99 mmHg Diasolic)	Start/ add long acting DHP CCB (See Appendix C). Gradually increase dose to control BP up to maximum dose. If partial or no control and still moderate hypertension, see Persistent Moderate Hypertension.	First occurrence: Continue cediranib at full dose or decrease dose by one level Second occurrence: Decrease cediranib dose by one level
	Grade 2-Persistent Moderate Hypertension Stage 1 hypertension: (140-159 mmHg Systolic or 90-99 mmHg Diasolic) Recurrent or persistent \geq 24- 48 hrs);	Start/ add long acting DHP CCB (See Appendix C). Gradually increase dose to control BP up to maximum dose. If partial or no control and still moderate hypertension, add an additional drug and increase dose until BP control up to maximum dose.	Hold cediranib and add additional drugs. Restart cediranib at one lower dose level (when controlled).
	Grade 3 Stage 2 hypertension (systolic \geq 160 mmHg or diastolic \geq 100 mmHg);	If asymptomatic : Hold cediranib and start immediate antihypertensive therapy with 2 drug combination including at least a DHP CCB. Increase dose until BP control up to maximum dose of both agents. If partial or no BP control, add another drug up to 4; increase to optimal or maximal doses on all drugs.	First occurrence: Hold cediranib until blood pressure within Stage 1 hypertension range (systolic 140-159 mmHg or diastolic 90-99 mmHg); and decrease cediranib dose by one level Second occurrence: Hold cediranib until blood pressure within Stage 1

		If symptomatic: stop cediranib, hospitalize with aggressive IV therapy as per hypertensive crisis management	hypertension range (systolic 140-159 mmHg or diastolic 90-99 mmHg); and either decrease cediranib by one dose level or stop cediranib permanently
	Grade 4 Life-threatening consequences (e.g. malignant hypertension, transient or permanent neurological deficit, hypertensive crisis); urgent intervention indicated	Stop cediranib, hospitalize with aggressive IV therapy as per hypertensive crisis management.	Stop cediranib permanently

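### Section 6.1.1 and Appendix C give conflicting cediranib instructions for Grade 2 hypertension, and neither is said to govern

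*Combined protocol and SAP*

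**What the plan says.** Instructions on cediranib in Grade 2 hypertension stand in three places.

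- **Section 6.1.1, table.** Grade 2-Mild: "First occurrence: Continue cediranib at full dose or decrease dose by one level", then "Second occurrence: Decrease cediranib dose by one level". Grade 2-Persistent Moderate has the same pressure range but is recurrent or lasts at least 24-48 hours. There cediranib is held, drugs are added, and cediranib restarts one level lower once pressure is controlled.
- **Appendix C, table.** Grade 2-Mild: start or increase antihypertensives, with cediranib unchanged. The Persistent Moderate row reads "If partial or no control and BP still in a moderate range for 24-48 hours, hold". What is held is cediranib; the row then has antihypertensives added and raised until pressure comes under control, and takes the study drug down one level.
- **Appendix C, notes.** "Patients may have up to 2 drugs for management of hypertension prior to any dose reduction in" cediranib. Also: "24-48 hours should elapse between modifications of antihypertensive therapy". A further note ends protocol therapy if more than two dose reductions are needed.

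Section 6.1 refers the reader to Appendix C for specific guidelines. Neither text says which prevails where they differ. The Phase II dose levels in Section 6 are 30, 20 and 15 mg daily.

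**The concern.** A site that follows Section 6.1.1 and a site that follows Appendix C can treat the same blood pressure history differently and both be compliant. Cediranib is given in both Phase II arms, and the cediranib risk list in Section 7.1.1 places hypertension in its most frequent category (above 20%), so sites can expect to use these tables. That category covers hypertension in general, so it does not give the frequency of the Grade 2 situations in dispute.

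The stakes are the dose received, the number of permitted reductions used up, and possibly time on protocol therapy. In an open-label trial with progression-free survival as the primary endpoint, variation in dose that arises only from which page a site reads is avoidable.

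**Working it through.** The plan states no figure to reproduce on this point. The check sets the texts side by side for a patient at the full 30 mg dose.

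| Situation | Section 6.1.1 | Appendix C row | Appendix C two-drug note |
|---|---|---|---|
| 1. First Grade 2-Mild episode | 30 or 20 mg | 30 mg | Allows 30 mg |
| 2. Second Grade 2-Mild episode, on one antihypertensive | 20 mg | 30 mg | Allows 30 mg |
| 3. 145/92 mmHg, on one antihypertensive, still present after 48 hours | Hold, then 20 mg | Hold, then 20 mg | Allows a second drug before reduction; effect on this row not stated |

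**Situation 1.** Section 6.1.1 leaves a choice ("Continue cediranib at full dose or decrease dose by one level"). A site that keeps the full dose satisfies both tables. A site that reduces follows Section 6.1.1 but departs from the Appendix C row.

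**Situation 2.** This is the direct contradiction. Section 6.1.1 requires a decrease, while the Appendix C row for the same grade changes nothing and does not distinguish occurrences. No single action satisfies both.

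**Situation 3.** The two tables agree with each other, and neither makes the number of drugs a condition. The uncertainty comes from the note, which can be read in two ways. It may mean only that two drugs can be in place before the reduction takes effect. The second drug is then added during the hold, and the patient restarts at 20 mg. Or it may mean that a second drug can be tried before a reduction is called for. A patient controlled on two drugs would then stay at 30 mg. The text does not choose between these readings.

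**Grade 3.** The tables agree for a first asymptomatic episode that comes under control. Appendix C says "Start immediate therapy with 2 drug combination including at least a DHP CCB", and both tables hold cediranib and resume one level lower. Only the unstated scope of the note is open there.

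**Size of the difference in dose.** One level from full dose is (30 - 20) / 30 = 33%.

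**Count of reductions.** The levels 30, 20 and 15 mg allow two reductions. In situation 2, a patient kept at full dose after the first episode has used one of the two under Section 6.1.1 and none under the Appendix C row. If the optional first-occurrence decrease was also taken, and the second counts from the current dose, both are used (30 to 20 to 15 mg), against none under Appendix C.

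**The case against.** The strongest reply is that the provisions can be combined. A reader might infer that the two-drug allowance and the 24-48 hour hold are mutually exclusive, since the spacing between antihypertensive changes equals the period that triggers the hold. The documents do not support that:

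- The note concerns dose reductions, and a hold is not a reduction. Both tables add drugs during the hold. Section 6.1.1 places the lower dose at restart, after control.
- The note is permissive. It does not require either drug to be raised to its maximum, and the Appendix C row allows either doses or the number of drugs to be increased. With 24-hour spacing, a second drug can be added inside a 48-hour window. Counting days of stepwise titration therefore shows no conflict.
- The first-occurrence decrease at Grade 2-Mild is optional, so by itself it contradicts nothing.

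All of this stands, and it removes any claim of impossibility. It does not settle how the note bears on the persistent row, and it does not touch situation 2.

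One could also argue that a second mild episode belongs in the persistent row, because Section 6.1.1 includes recurrent hypertension there. The Appendix C hold, however, depends on pressure remaining in range for 24-48 hours. A recurrence controlled sooner stays in its mild row with cediranib unchanged.

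Finally, both arms share the same hypertension rules, and nothing in the documents shows an effect that differs by arm. That also stands.

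**Conclusion.** The concern holds as an inconsistency in the instructions for Grade 2 hypertension. The firmest part is the second Grade 2-Mild occurrence, where one text requires a decrease and the other leaves the dose alone. The optional decrease at the first occurrence and the unstated scope of the two-drug note in persistent moderate hypertension add to it.

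The same patient can be at 30 or 20 mg, a difference of one third, and can have used one more or one fewer of the two reductions allowed before protocol therapy ends. This assumes a patient at the full dose and both texts in force together, which follows from the cross-reference in Section 6.1 and the absence of a precedence rule.

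A reader might go further and infer a biased comparison of progression-free survival. The documents give no frequency for these situations and no mechanism that differs by arm, so the effect on progression-free survival is not quantified. The planned sample size, number of events and significance level are unaffected. The point should be corrected, but it does not undermine the design.

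**What to change.** Reconcile the Section 6.1.1 table, the Appendix C table and the Appendix C notes on four items:

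1. cediranib at the first Grade 2-Mild occurrence;
2. cediranib at the second Grade 2-Mild occurrence;
3. the order of hold, added drugs and dose reduction in persistent moderate hypertension;
4. the grades and rows to which the two-drug note applies, and whether control on two drugs affects the reduction.

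Then keep one sequence in one place and refer to it from the other, or state which text governs. Which clinical rule is right is for the sponsor and investigators to decide; this review does not propose one.

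The cost is wording in two tables and their notes, issued as an amendment. There is no change to the sample size or the analysis.

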APPENDIX D

Collection/Recording of Blood Pressure Information

1.0 General Guidelines

- 1.1 Frequency of monitoring. Blood pressure (BP) should be monitored weekly during the first cycle of cediranib therapy, then at least every 2 weeks for the duration of treatment. More frequent monitoring may be considered on a study by study basis, particularly during the first two cycles of cediranib therapy.
- 1.2 Data recording. All required data should be recorded in the appropriate CRF or on the patient's blood pressure monitoring diary, as appropriate. **The following data are required at baseline and at each subsequent assessment:**
 - Assessment date and time
 - Pulse
 - Systolic and diastolic BP (2 readings/assessment taken 5 minutes apart while patient sitting)
- 1.3 Risk factors for hypertension (assess and record data in baseline history/physical CRF)
 - Diabetes (type 1 or type 2)
 - Renal disease (specify on CRF)
 - Endocrine condition associated with HTN (specify on CRF)
 - Use of steroids or NSAIDs (specify all concomitant meds)
 - Underlying cardiovascular condition – specify (*i.e.*, ischemic heart disease)

2.0 Baseline data collection (at study entry)

- 2.1 All patients
 - Current BP
 - Proteinuria, if present
- 2.2 Patients with preexisting hypertension (*i.e.*, those for whom “hypertension” is entered as a concomitant condition at study entry, or those who are currently receiving therapy with antihypertensive medication) – also record:
 - Date of HTN diagnosis (original)
 - Type HTN (essential or secondary)
 - CTCAE v5.0 grade of HTN (at time of study entry)
 - Trade name, drug class*, dose, dose frequency, start/stop dates/ongoing of the following:
 - Antihypertensive agents taken at study entry
 - Antihypertensive agents taken in past (e.g., discontinued for toxicity, lack of efficacy)

3.0 Follow up BP data collection (during study)

- 3.1 All patients (at each clinic visit)

- Current BP
 - Proteinuria, if present
- 3.2 Patients with treatment-emergent hypertension [defined as BP increase of >20 mmHg (diastolic) OR BP >150/100 (if previously within normal limits)] – record at time of hypertension diagnosis and at all subsequent clinic visits:
- BP changes from baseline (or from previous assessment) (specify CTCAE v5.0 grade changes)
 - Hypertension-related symptoms as reported by patient (*e.g.*, headache)
 - Other relevant changes associated with development of hypertension (*e.g.*, ECG abnormalities)
 - Trade name, drug class*, dose, dose frequency, start/stop dates/ongoing of currently prescribed antihypertensive agents
- 3.3 Patients with preexisting hypertension at study entry – record at each clinic visit
- BP changes from previous clinic visit (specify CTCAE v5.0 grade changes)
 - Hypertension-related symptoms reported by patient (*e.g.*, headache)
 - Other relevant changes associated with development of hypertension (*e.g.*, ECG abnormalities)
 - Changes in antihypertensive medications since last assessment (*e.g.*, dose change, add/discontinue drug)

Classes of antihypertensive drugs include ACE inhibitors, calcium channel blockers, alpha blockers, beta blockers, diuretics, angiotension II receptor antagonists.

APPENDIX E

CTEP MULTICENTER GUIDELINES

If an institution wishes to collaborate with other participating institutions in performing a CTEP sponsored research protocol, then the following guidelines must be followed.

Responsibility of the Protocol Chair

- The Protocol Chair will be the single liaison with the CTEP Protocol and Information Office (PIO). The Protocol Chair is responsible for the coordination, development, submission, and approval of the protocol as well as its subsequent amendments. The protocol must not be rewritten or modified by anyone other than the Protocol Chair. There will be only one version of the protocol, and each participating institution will use that document. The Protocol Chair is responsible for assuring that all participating institutions are using the correct version of the protocol.
- The Protocol Chair is responsible for the overall conduct of the study at all participating institutions and for monitoring its progress. All reporting requirements to CTEP are the responsibility of the Protocol Chair.
- The Protocol Chair is responsible for the timely review of Adverse Events (AE) to assure safety of the patients.
- The Protocol Chair will be responsible for the review of and timely submission of data for study analysis.

Responsibilities of the Coordinating Center

- Each participating institution will have an appropriate assurance on file with the Office for Human Research Protection (OHRP), NIH. The Coordinating Center is responsible for assuring that each participating institution has an OHRP assurance and must maintain copies of IRB approvals from each participating site.
- Prior to the activation of the protocol at each participating institution, an OHRP form 310 (documentation of IRB approval) must be submitted to the CTEP PIO.
- The Coordinating Center is responsible for central patient registration. The Coordinating Center is responsible for assuring that IRB approval has been obtained at each participating site prior to the first patient registration from that site.
- The Coordinating Center is responsible for the preparation of all submitted data for review by the Protocol Chair.
- The Coordinating Center will maintain documentation of AE reports. There are two options for AE reporting: (1) participating institutions may report directly to CTEP with a copy to the Coordinating Center, or (2) participating institutions report to the Coordinating Center who in turn report to CTEP. The Coordinating Center will submit AE reports to the Protocol Chair for timely review.

- Audits may be accomplished in one of two ways: (1) source documents and research records for selected patients are brought from participating sites to the Coordinating Center for audit, or (2) selected patient records may be audited on-site at participating sites. If the NCI chooses to have an audit at the Coordinating Center, then the Coordinating Center is responsible for having all source documents, research records, all IRB approval documents, NCI Drug Accountability Record forms, patient registration lists, response assessments scans, x-rays, etc. available for the audit.

Inclusion of Multicenter Guidelines in the Protocol

- The protocol must include the following minimum information:
 - The title page must include the name and address of each participating institution and the name, telephone number and e-mail address of the responsible investigator at each participating institution.
 - The Coordinating Center must be designated on the title page.
 - Central registration of patients is required. The procedures for registration must be stated in the protocol.
 - Data collection forms should be of a common format. Sample forms should be submitted with the protocol. The frequency and timing of data submission forms to the Coordinating Center should be stated.
 - Describe how AEs will be reported from the participating institutions, either directly to CTEP or through the Coordinating Center.
 - Describe how Safety Reports and Action Letters from CTEP will be distributed to participating institutions.

Agent Ordering

- Except in very unusual circumstances, each participating institution will order DCTD-supplied agents directly from CTEP. Agents may be ordered by a participating site only after the initial IRB approval for the site has been forwarded by the Coordinating Center to the CTEP PIO.

